6 SAMPLE SIZE

6.1 Preliminary Data

Sample size calculations were based on comparisons of in-person ESTEEM to waitlist for CAS²⁹ and meta-analytic effect sizes of iCBT compared to weak control conditions for depression.³¹⁻³⁴

6.2 Sample Size Determination for the Primary Outcome

Assigning 60 YMSM to each condition (iCBT vs. self-monitoring) and accounting for 20% attrition, a liberal estimate based on our previous online RCT attrition of 0-17%, will provide \geq 80% chance of detecting a difference ($p < .05$) between the conditions of $d = .40$, which is lower than we found when comparing in-person ESTEEM to waitlist ($d = .59$ for CAS).²⁹ While we likely do not have power to detect changes in our biologic HIV/STI outcomes, including them 1)

STATISTICAL ANALYSIS PLAN

verifies study eligibility, 2) establishes self-testing protocols for our future research, and 3) promotes public health.

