A total of 120 YMSM participants will be enrolled in this study ($n = 60$ per condition). Assigning 60 participants to each condition (iCBT vs. self-monitoring) and accounting for 20% attrition, a liberal estimate based on our previous online RCTs (i.e., 93-100%), will provide $\geq 80\%$ chance of detecting a difference ($p < .05$) between the conditions of $d = .40$, which is significantly lower than what we found when comparing in-person ESTEEM to waitlist ($d = .59$ for CAS, $d = .55$ for depression) and lower than even the smallest average meta-analytic effect ($d = .66$) of iCBT compared to weak control conditions for depression. While we likely do not have power to detect changes in our biologic HIV/STI outcomes, including them 1) verifies study eligibility, 2) establishes self-testing protocols for our future adequately powered research, and 3) promotes public health. For Aim 3, a total of 55 participants, including ($n = 20$) Aim 2 participants, ($n = 6$) study therapists and supervisors, ($n = 8$) government administrators and leadership, ($n = 7$) LGBTQ community organization staff, and ($n = 7$) medical providers will be interviewed in order to identify themes in regard to barriers and facilitators of implementing iCBT ESTEEM among Chinese YMSM.

Study Design

Aim 2 of the proposed prospective study will follow a 2-arm RCT design where 120 Chinese YMSM participants will be randomly assigned to one of two conditions:

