7.2 Planned Analyses

Our primary hypothesis is that Chinese ESTEEM iCBT will yield significantly greater reductions in CAS and HIV risk behavior than weekly self-monitoring. Repeated measures intent-to-treat generalized linear mixed models (GLMM) with negative binomial distributions and maximum likelihood estimation will be fit to CAS at 4- and 8-month follow-up adjusted for baseline CAS with intervention arm as a covariate. We will test the best-fitting correlation structure, but based on our previous studies, expect it to be compound symmetrical. We will conduct exploratory analyses to determine within- and across-condition effects of each arm over time, including appropriate parameters for any trends evident over time. These models may be adjusted for any potential covariates (e.g., urban vs. rural residence; level of outness or education) that are associated with our outcomes if the intervention arms are not balanced on these variables.

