4.1 Primary Outcome

The primary outcome is past-30-day condomless anal sex with main or casual partners at 8-month follow-up assessed via Timeline Follow-Back.

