5. RANDOMIZATION

5.1 Method of Randomization

Randomization occurred on the participant level. Participants were randomly assigned to receive one of two conditions: iCBT ESTEEM or self-monitoring (N = 120). We used a 1:1 randomization scheme such that for every one participant randomized to iCBT ESTEEM, one participant was randomized to self-monitoring. Participant randomization was stratified based on mental health (i.e., eligible based on depressive symptoms, anxiety symptoms, or both based on the Brief Symptom Inventory-4). Stratified randomization occurred using a random number table generated by SPSS such that 60 participants were randomized to each condition.

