8.3 Analysis of Primary Outcome: HIV-Risk Behavior (Condomless Anal Sex)

Analysis	Primary analysis of primary outcome: Number of past-30-day condomless anal sex (CAS) acts with primary or casual partners as measured by the Timeline Follow-Back at the 8-month follow-up assessment.
Analysis population	All randomized participants
Endpoint	8-month follow-up
Unit of analysis	Participant
Method of analysis*	We will use repeated measures generalized linear mixed models with maximum likelihood estimation to test whether receipt of ESTEEM iCBT vs self-monitoring affects changes in the number of past-30-day CAS with primary or casual partners from baseline to 8-month follow up. We will use a contrast to test condition x time comparisons. We will test the best-fitting correlation structure, but based on our previous studies, expect it to be compound symmetrical. In the event of high skew or zero inflation, the appropriateness of modeling a negative binomial or Poisson distribution will be considered.
Handling of missing data	MAR assumption
Adjustment covariates	Adjustment for baseline covariates not balanced at randomization
Type I error	5% (2-sided)
Control of type I error	None

STATISTICAL ANALYSIS PLAN

Treatment effect estimate	Odds ratio with 95% confidence limits
---------------------------	---------------------------------------

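### The stated ≥80% power for d = .40 does not follow from SAP 6.2's inputs; the planned 8-month contrast has about 37–71% at assumed correlations of .3–.7

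*SAP*

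**What the plan says.** SAP 6.2 gives the sample size as "Assigning 60 YMSM to each condition (iCBT vs. self-monitoring) and accounting for 20% attrition", and claims at least an "80% chance of detecting a difference ($p < .05$) between the conditions of $d = .40". It sets this against the in-person ESTEEM effect of d = .59 on condomless anal sex (CAS). The protocol repeats the claim in the Synopsis (Number of Participants), 5.2 and 7.1: "chance of detecting a difference ($p < .05$) between the conditions of $d = .40$, which is significantly lower than what we found". The retention paragraph of Protocol 5.4 gives the same assurance without the number.

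The two documents plan different primary analyses:

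- **SAP 4.1 and 8.3.** The primary outcome is "past-30-day condomless anal sex with main or casual partners at 8-month follow-up assessed via Timeline Follow-Back". The model addresses change from baseline to 8 months, and "We will use a contrast to test condition x time comparisons". The test is two-sided at 5%. CAS at 4 months is secondary.
- **Protocol 7.2.** Negative binomial mixed models "will be fit to CAS at 4- and 8-month follow-up adjusted for baseline CAS with intervention arm as a covariate", so both follow-ups contribute.

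Both expect a compound symmetric correlation structure. Neither gives a value for the correlation, a mean or dispersion for CAS, or the method behind the 80%.

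**The concern.** Sixty per arm less 20% is 48. That is a small sample for d = .40, and the usual two-sample calculation falls far short of 80%. Repeated measures can raise power, but how much depends on the within-person correlation and on which contrast is tested. The SAP keeps the protocol's power figure while making 8 months the sole primary time point.

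This is the only power statement for the primary outcome. It tells readers that the trial can detect an effect well below the earlier in-person one. If it is wrong, a non-significant 8-month result will be read as stronger evidence against a moderate effect than it is.

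**Working it through.** **Inputs from the documents.** Sixty per arm, 1:1 (SAP 5.1, 6.2). Attrition 20%, so 60 × 0.80 = 48 evaluable per arm. d = .40. Two-sided 5% (SAP 8.3). Compound symmetry (SAP 8.3, Protocol 7.2).

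**Assumptions.** The within-person correlation ρ is not given, so a range of .3 to .7 is shown. d is in cross-sectional SD units. CAS is treated as continuous.

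**Formula.** Power comes from the noncentral t with 2n − 2 degrees of freedom and noncentrality λ = (d/√f) × √(n/2), where f is the variance of the analysed quantity relative to the cross-sectional variance.

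**Step 1: try to reproduce the 80% from the stated inputs (f = 1).** For n = 48, λ = 0.40 × √24 = 1.96.

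| Variant | Power at d = .40 |
|---|---|
| 48 per arm, two-sided | 49% |
| 48 per arm, one-sided | 62% |
| 60 per arm (no attrition), two-sided | 58% |
| 60 per arm, one-sided | 70% |

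None reaches 80%. With 48 per arm, two-sided, 80% power needs d = .58; with 60 per arm, d = .52.

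**Step 2: the SAP's primary contrast.** The variance of the change from baseline to 8 months is 2(1 − ρ) in cross-sectional units, so f = 2(1 − ρ).

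| ρ | f | λ (48/arm) | Power, 48/arm | d for 80% power, 48/arm | Power, 60/arm |
|---|---|---|---|---|---|
| .3 | 1.4 | 1.66 | 37% | .68 | 45% |
| .5 | 1.0 | 1.96 | 49% | .58 | 58% |
| .7 | 0.6 | 2.53 | 71% | .45 | 80% |

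Eighty per cent at d = .40 needs ρ of about .76 with 48 per arm, and about .70 even with no attrition.

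**Step 3: could the planned handling of missing data close the gap?** Maximum likelihood keeps the baseline records of dropouts. With 60 baseline and 48 follow-up records per arm, power is 40%, 51% and 72% at ρ = .3, .5 and .7, and about .75 is needed for 80%. If d were instead in units of the SD of change, power would be 49% whatever the correlation.

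**Step 4: the protocol's model.** Take it as a test on the mean of the two follow-ups, adjusted for baseline. The mean has variance (1 + ρ)/2 and covariance ρ with baseline, so f = (1 + ρ)/2 − ρ².

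| ρ | f | Power, 48/arm |
|---|---|---|
| 0 | 0.500 | 78% |
| .25 | 0.5625 | 73% (minimum) |
| .3 | 0.560 | 74% |
| .5 | 0.500 | 78% |
| .54 | 0.478 | 80% |
| .7 | 0.360 | 90% |

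This model reaches 80% at ρ of about .54.

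**The case against.** The best case for the plan has four parts.

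- **The protocol's model can support its claim.** It reaches 80% at a correlation of about .54 and 90% at .7. With no attrition it exceeds 80% even at its weakest correlation (83% at .25). This stands: in the protocol the fault is an unstated assumption, not a figure shown to be impossible. It does not carry over to SAP 6.2, because the SAP tests 8 months alone.
- **SAP 8.3 might be read more favourably.** It does not say whether baseline is adjusted for or constrained. A baseline-adjusted 8-month comparison (f = 1 − ρ²) would have 53%, 61% and 78% power at correlations of .3, .5 and .7. That beats the change contrast but still needs about .72 for 80%, and the SAP does not specify it.
- **CAS is a count.** The protocol plans a negative binomial model and the SAP may use one, so a standardised difference is only an approximation. That is true, but the documents state the claim as d and give no mean or dispersion, so 80% cannot be verified on the count scale either.
- **The practical effect is limited.** The objective is preliminary efficacy, the SAP reports 120 already enrolled, and the confidence interval will show the precision achieved. This is a reason not to change the design. It is not a reason to leave an unsupported power figure in place.

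**Conclusion.** The concern holds. The stated ≥80% does not follow from the inputs beside it: those give about 49%. For the SAP's planned baseline-to-8-month contrast, power at d = .40 is about 37–71% over correlations of .3–.7, and 80% requires about .76, which is stated nowhere. The chance of missing a true d = .40 is therefore about 29–63% over that range, rather than 20% or less. At a correlation of .5 the effect detectable with 80% power is about d = .58, essentially the earlier in-person effect of .59 that the SAP says it can go below.

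These figures assume compound symmetry, d in cross-sectional SD units, 48 completers per arm and a continuous outcome; power for an overdispersed count could differ. The conclusion is not that 80% is unattainable under every model. It is that the plan states no assumption under which its primary test attains it.

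**What to change.** Leave enrolment, endpoint, test and alpha alone.

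**SAP 6.2.** Replace the power claim with text such as:

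> Forty-eight evaluable participants per arm give 80% power for d of about 0.58 and about 49% power for d = 0.40 (two-sided 5%, unadjusted; the baseline-to-8-month contrast has the same power at an assumed correlation of 0.5). Power of 80% at d = 0.40 would require a correlation of about 0.76. CAS is treated as continuous.

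If the sponsor holds a correlation and method that support 80% for the 8-month contrast, state those instead.

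**Protocol Synopsis, 5.2 and 7.1.** Restate the power for the 7.2 model with its assumed correlation (about 78% at 0.5, 80% at about 0.54), or refer to the corrected SAP figure. Align the assurance in 5.4.

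The cost is wording only, and a less favourable power figure.

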- 1) **ESTEEM iCBT:** This online CBT treatment consists of 10 weekly modules that participants will complete over the course of 10 weeks. Modules contain weekly psychoeducational text and vignettes about minority stress and mental health; brief videos illustrating the CBT skills; and homework exercises that therapists review and provide feedback on. Homework exercises include weekly tracking of stress and mood, practicing new skills (e.g., mindfulness, cognitive restructuring), and exercises related to considering the origins of stress and negative emotions that participants may be experiencing. Therapists provide feedback after each homework assignment, including reviewing each participant's treatment goals as part of the first session's homework. Therapists who support this condition will be instructed to incorporate SGM-specific content and feedback into homework reviews. In the US, modules were adapted directly from the in-person materials (e.g., therapist manual, participant handouts) used in our previously successful trials of this treatment. The treatment has also been recently culturally adapted for in-person treatment among Chinese YMSM and found to be acceptable and feasible.
- 2) **Self-monitoring control:** In this control condition, participants will be asked to indicate their past 7-day mood, stress experiences, and mental and behavioral health on an online survey. This type of self-monitoring has been shown to yield improvement in behavioral health outcomes. Self-reporting SGM stress experiences has also been shown to produce reductions in depression symptoms over time. Participants will record these experiences once per week for 10 weeks.

Prior to randomization, participants will complete an online screener, video screener on WeChat, at-home HIV/STI testing kit for HIV and syphilis, and consent call on WeChat (see Section 6.1 Study Procedures for more information about these steps of the study). For the at-home HIV/STI testing kit for HIV and syphilis, rapid test results will be ready to be read by participants in 20 minutes. HIV/STI test results will be discussed with participants by study counselors during the same day as testing via WeChat. A CSU research team member will contact participants on WeChat after 5 business days of sending the HIV/STI testing kit if the participant has not sent the CSU team a photo of their results. Specific procedures regarding risks for the at-home HIV/STI testing is outlined in Section 2.2.

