1.2 Prior Experience (if applicable)

Our ESTEEM treatment for the proposed training has been previously developed and tested by the current research team. In the pilot testing of the treatment among a sample of gay and bisexual men³⁷, the treatment significantly reduced depressive, alcohol use problems, sexual compulsivity, and past-90-day condomless sex with casual partners, as well as improved condom use self-efficacy. The treatment yielded moderate and marginally significant improvements compared to a waitlist group in anxiety symptoms and past-90-day heavy drinking. Effects were generally maintained at follow-up.

Since the pilot, the research team has been in the process of testing the efficacy of the treatment among gay and bisexual men in an RCT against Community Mental Health Treatment and Voluntary Testing and Counselling for HIV (see IRB protocol: 1509016430). The research team has also adapted the SGM-affirmative CBT treatment for gender diverse, sexual minority women (see IRB protocol: 2000020997),³⁶ as well as for an online platform (see IRB protocol: 2000025803).

In terms of the cultural adaptation of the treatment, we have culturally adapted the in-person ESTEEM intervention (and measures) for Chinese YMSM over the past year across an 8-stage adaptation process with YMSM and stakeholders ($n = 56$), including a small open pilot with Chinese YMSM ($n = 8$). We also worked with our colleagues in Sweden at the Karolinska Institutet – world leaders in internet-based CBT (iCBT) – to create an iCBT version of ESTEEM. iCBT combines a self-guided interactive mobile web-platform with brief counselor feedback and online exercises and homework, requiring 80% less counselor time than in-person ESTEEM; caseloads can reach 200-300 per counselor. In a small US pilot ($n = 10$), iCBT ESTEEM was highly functional (see IRB protocol: 2000025803). Thus, we have incorporated these advances in the proposed study to develop Chinese ESTEEM iCBT – a highly efficient, private intervention that addresses minority stress and mental health as HIV prevention. Its mobile platform overcomes stigma-related barriers to broadly reach YMSM while still retaining in-person ESTEEM's robust ability to reduce YMSM's HIV risk.

2 Rationale/Significance

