We have used these retention strategies previously to attain very high retention in our online RCTs. [name] attained 100% retention with 77 YMSM in his first online RCT. [name] also retained 88% of participants at follow-up in an online HIV-prevention RCT in Romania. Using near-identical strategies as will be used here, [name] retained 83% of YMSM in her in-person motivational interviewing-based HIV-prevention RCT in Hunan. We estimate that we will retain at least 80% of participants, a quite liberal goal given that we have exceeded this goal in our previous studies with YMSM in high-stigma contexts. Nonetheless, our study is powered with even 20% attrition, to detect effects smaller than those found for identical outcomes (e.g., condomless anal sex, depression) in our previous RCTs with YMSM.

Qualitative Interviews: For the interviews conducted with LGBTQ organization staff, government administrators and leadership, and medical providers, the PI at CSU and her research team will contact the governmental and NGO professionals in their network about participating in these interviews. All participants will be compensated 200 RMB (\$31.48) for their participation in interviews.

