Intervention	
1) ESTEEM iCBT: This online CBT treatment consists of 10 weekly modules that participants will complete over the course of 4 months. Modules contain weekly psychoeducational text and vignettes about minority stress and mental health; brief videos illustrating the CBT skills; and homework exercises that therapists review and provide feedback on. Homework exercises include weekly tracking of stress and mood, practicing new skills (e.g., mindfulness, cognitive restructuring), and exercises related to considering the origins of stress and negative emotions that participants may be experiencing. Therapists provide feedback after each homework assignment, including reviewing each participant's treatment goals as part of the first session's homework. Therapists who support this condition will be instructed to incorporate LGBTQ-specific content and feedback into homework reviews. This intervention was culturally adapted for Chinese YMSM and found to be acceptable and feasible.
 
2) Self-monitoring control: In this control condition, participants will be asked to indicate their past 7-day mood, stress experiences, and mental and behavioral health on an online survey. Participants will record these experiences once per week for 10 weeks.

Duration of Intervention	10 weekly modules in up to 17 weeks (four months)
Primary Outcome	Number of past-30-day condomless anal sex (CAS) acts with primary or casual partners as measured by the Timeline Follow-Back at the 8-month follow-up assessment.
Primary Analysis	We will examine the efficacy of the intervention using a generalized linear mixed model to test whether receipt of ESTEEM iCBT vs the self-monitoring control affects changes in the number of past-30 day CAS with primary or casual partners from baseline to 8-month follow up.

STATISTICAL ANALYSIS PLAN

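### The CAS benchmark (d = .59) behind the primary-outcome power statement appears to come from a different measure and comparator, and without unstated correlation gains the stated power needs an effect about that large

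*SAP*

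**What the plan says.** SAP 6.1 gives the basis of the calculation: "Sample size calculations were based on comparisons of in-person ESTEEM to waitlist for CAS". SAP 6.2 starts from "Assigning 60 YMSM to each condition (iCBT vs. self-monitoring) and accounting for 20% attrition", claims at least 80% power at d = .40, and adds that this target is one "which is lower than we found when comparing in-person ESTEEM to waitlist", where d was .59 for CAS. The same comparison stands in the Protocol Synopsis and in Protocol 5.2 and 7.1. Protocol 5.4 goes further and says that the study is powered "to detect effects smaller than those found for identical outcomes (e.g., condomless anal sex, depression) in our previous RCTs with YMSM".

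The earlier trial is the in-person pilot against a waitlist; Protocol reference 37 and SAP reference 29 are the same paper. In describing it, Protocol 1.2 reports one condomless-sex outcome: "past-90-day condomless sex with casual partners".

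The primary outcome here, in the SAP Study Summary and SAP 8.3, is "Number of past-30-day condomless anal sex (CAS) acts with primary or casual partners" at 8 months. CAS with casual partners only is a separate, secondary outcome (SAP 4.2). Of the control condition, the Protocol (Synopsis and Section 4) says: "This type of self-monitoring has been shown to yield improvement in behavioral health outcomes".

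**The concern.** A standardized effect divides a difference by the standard deviation of its own measure, so it does not carry over to a count with another recall window and partner mix. Neither document gives a mean, standard deviation, dispersion or proportion of zeros for the 30-day count, so nothing in them supports the transfer. Entry requires CAS in the past 3 months (Protocol 5.3), so some men may well report none in a 30-day window.

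What is at stake is how an 8-month null result is read. If readers accept that the trial could detect effects smaller than one already seen on the same outcome, a null result will look like evidence against an effect of that size.

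**Working it through.** **1. The two measures side by side.**

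| | Earlier trial (Protocol 1.2) | This trial (SAP Study Summary, 8.3) |
|---|---|---|
| Recall window | 90 days | 30 days |
| Partners | casual | primary or casual |
| Comparator | waitlist | weekly self-monitoring |
| Delivery | in person | online |

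No section prints a window or partner type next to .59. The link rests on Protocol 1.2 and the shared citation.

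**2. The plan's own power figure.** Inputs: 60 per arm and 20% attrition (SAP 6.2), so n = 60 × 0.8 = 48 per arm; two-sided 5% (SAP 8.3); d = .40.

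- Normal approximation: power = Φ(d√(n/2) − 1.96) = Φ(.40 × √24 − 1.96) = Φ(0.00) = 50%. The t-test gives 49%.
- With no attrition (60 per arm) the t-test gives 58%.
- Smallest d with 80% power at 48 per arm: (1.96 + 0.842) × √(2/48) = .57; t-test, .58.
- At d = .59 the t-test gives 82%.

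The stated figure of at least 80% at d = .40 is therefore not reproduced by a simple comparison. The variance would have to shrink to .40² × 24 / 2.802² = .489 of its unadjusted value. What that requires, for within-person correlation r under compound symmetry:

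- 8-month comparison adjusted for baseline: 1 − r² = .489, so r ≈ .71.
- Change from baseline to 8 months: 2(1 − r) = .489, so r ≈ .76.
- Baseline-adjusted mean of both follow-ups: (1 + r)/2 − r² = .489, so r ≈ .52. The primary endpoint, however, is the 8-month value alone.

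Neither document states a correlation, only the expected structure.

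**3. What the shorter window alone does to .59.** Assumptions, none from the documents: gamma-Poisson counts; mean 0.5, 1, 2 or 4 acts per 30 days; gamma shape 0.5, 1 or 2; at least one act in a 90-day baseline window; the same rate ratio (RR) in both windows. For person-level rates with mean M and variance V per 30 days, a window of t × 30 days has control mean tM and variance tM + t²V, treated mean tM·RR and variance tM·RR + t²V·RR². Then d = tM(1 − RR) / √(average of the two variances). RR is set to give d = .59 at t = 3, and d is recomputed at t = 1.

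- Lowest setting (mean 0.5, shape 2): M = .604, V = .133, RR = .523. At 30 days the means are .604 and .316 and the variances .737 and .352, so d = .288/√.544 = .39.
- Highest setting (mean 4, shape 0.5): M = 4.96, V = 35.4, RR = .438. The means are 4.96 and 2.17 and the variances 40.3 and 9.0, so d = 2.79/√24.65 = .56.
- Of the 12 settings, 11 give d of at least .40.

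**4. What adding main-partner acts could do**, in the lowest setting:

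- If they double every man's rate and respond with the same RR: means 1.208 and .632, variances 1.739 and .777, so d = .576/√1.258 = .51.
- If they form an independent count of the same size that does not respond, each variance rises by .737: d = .288/√1.281 = .25.

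The direction depends on facts that the documents do not give.

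**The case against.** The strongest reply is that the trial is designed for .40, not .59. The target is about a third below the benchmark, and the window calculation leaves it at or below the carried-over effect in 11 of 12 settings. That stands. A reader might infer from the mismatch that .40 is too optimistic, but the documents do not support this. Nor do they call .40 conservative; they say only that it is lower than .59, which is true.

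A reader might also put the window values into an unadjusted test with 48 per arm, get about 47% (d = .39) to 78% (d = .56), and blame the outcome mismatch for the loss. That would be wrong. The counts are assumed, and most of the shortfall arises because 80% power at .40 does not reproduce in that test. Baseline adjustment or repeated measures would raise power.

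Finally, a reader might take it as established that .59 is the 90-day casual-partner effect. Protocol 1.2 is a narrative summary and the paper cannot be checked here, so it remains an inference.

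Other mitigating points also stand. SAP 6.2 openly names in-person delivery and the waitlist. Protocol 1.2 reports that effects were generally maintained at follow-up. The statement about self-monitoring concerns behavioural health and does not mention CAS. Protocol 5.4 speaks of several earlier trials and gives CAS as an example. The stated aim is preliminary efficacy. None of this makes the CAS outcomes identical as the documents describe them, or supplies the missing correlation.

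**Conclusion.** The claim in Protocol 5.4 of power below effects found on identical outcomes is unsupported for CAS. On the documents' own description, recall window, partner type, comparator and delivery all differ from the earlier trial. The window and partner part depends on the inference that .59 belongs to the outcome in Protocol 1.2; the comparator and delivery differences do not.

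The mismatch alone neither changes the power figure nor refutes d = .40. Its weight comes from the sample size: with 48 per arm and no adjustment, 80% power needs d = .58, almost the borrowed .59. Unless a within-person correlation of about .7 or more is assumed for the 8-month comparison, adequate power depends on an effect of about that size carrying over to a different count and control. The t-test figures treat a skewed count as roughly normal, and the .39 to .56 range rests on assumed counts. This should be corrected before the results are interpreted; it does not call for a change of design.

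**What to change.** 1. In SAP 6.1 and 6.2 and Protocol 5.2, 5.4 and 7.1, state which CAS measure, recall window, partner type and comparator d = .59 refers to, after checking the source. Delete the reference to identical outcomes in Protocol 5.4.
2. Restate the primary-outcome sensitivity as the minimum detectable rate ratio at 8 months with 48 to 60 per arm, under the negative binomial model that Protocol 7.2 plans. Take the mean, zero fraction and dispersion from the baseline Timeline Follow-Back, pooled over arms and without arm labels, and state any correlation assumed. Because baseline counts come from men selected for recent CAS, show a lower mean as well.
3. Say that a null result excludes the earlier effect only so far as the 95% confidence interval does. That interval should be on the rate-ratio scale if a count model is used; SAP 8.3 at present lists an odds ratio.

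The cost is wording in two documents and one calculation on baseline data. N, endpoint and model stay as they are, since SAP Section 3 reports that all 120 were enrolled. The downside is that the stated sensitivity becomes less favourable.
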